5.2. MyoStrain® Testing Methodology

System setup and testing methodology will follow the Myocardial Solutions SENC User's Manual 4.1. The SENC MyoStrain® Test procedure is a quick and simple analysis which will require only one series of images. The importation of the images from the scanner and organization of these images is mostly automated and requires very minimal interaction to function correctly. The workflow of the SENC MyoStrain® test requires only one scan and analysis phase allowing the complete scan to be completed with 6 heartbeats after imaging planning without breath-holds.

1. Use Preview mode for discovery and planning

- Before the actual analysis begins, the operator will use Preview mode to perform image planning and ensure the scanner is looking in the correct location and the myocardium is being imaged properly.
- After using Preview mode, the operator will switch the mode to Strain before acquiring more images or beginning the exam by clicking the Strain button found above the Report section

2. Select one slice from the Image List

3. Identify view and locate end-systole

4. Draw epicardial and endocardial contours on the myocardium

- To ensure accurate analysis of any view of the heart, the operator will draw a contoured mesh around the heart tissue. The mesh will quantify the entire LV of the current view and automatically segment the heart using the standard AHA model. This is done by drawing a contour on both the epicardial and endocardial edges of the left ventricle. The mesh application should be performed on each slice/view available.
- NOTE: When computing the strain after segmenting the heart with a mesh, the strain measurements are restricted within the mesh.

5. Repeat steps 2-4 for each image in Image List

6. After all images have been analyzed, complete the report and Export to PDF

- The Report Page automatically composes a report from the various sources of information that are obtained during the analysis. This report can then be uploaded, exported as a PDF document, or printed out for review.

During the SENC MyoStrain® Test analysis, each mesh applied to the dataset will populate the appropriate model in the Measures section. The color legend in Figure 3 provides a basic guide to the meaning of each color. The coloring shown demarcates specific regions validated in published literature based on levels of myocardial function. Normokinetic defines strain < -17% while Akinetic defines strain > -10%. The numeric strain values for each segment and global measurements will also be displayed on the report. Alternative coloring schemes may be utilized depending on operator preference.

Figure 3: Color Legend for Strain Test

The Measures section SENC MyoStrain® exams will display resting strain, as well as global circumferential and longitudinal strain as shown in Figure 4.

Global MyoStrain Measures

Strain Measures			Traditional Measures		
	Raw	Normal		Raw	Index
Global Longitudinal Strain (GLS)	-21.8 %	(<-17)	LVEF	67.6 %	- (53-74)
Global Circumferential Strain (GCS)	-20.4 %	(<-17)	LVED Mass	87.2 g	- (39-75)
			LVES Mass	110.3 g	- (39-75)
			LVED Volume	156 ml	- (53-99)
			LVES Volume	50.5 ml	- (15-40)
			LV Stroke Volume	105.4 ml	- (35-63)

[figure not shown]
Resting MyoStrain Measures

Figure 4: Example Strain exam with 6 views quantified

5.3. Study Population

Subjects enrolled in the SURVIVE Registry and scheduled to undergo chemotherapy or targeted cancer treatment will be consented for possible inclusion in PROACT. Then the patient will be evaluated with a baseline MyoStrain® test to determine whether the patient exhibits moderate or high risk of developing cardiotoxicity. As a minimum, the inclusion and exclusion criteria listed below will apply.

5.4. Inclusion Criteria

- 1) Participant in the SURVIVE registry
- 2) Signed consent form for PROACT
- 3) Histological diagnosis of any cancer type (patients with treated and clinically stable brain metastasis are acceptable)
- 4) Scheduled to receive anti-cancer therapy (radiation therapy is permitted)

5.5. Exclusion Criteria

- 5) Contraindication to magnetic resonance imaging (MRI)
- 6) Unable to comply with study investigations (in the judgment of the investigator)
- 7) Life expectancy less than 1 year

Note: If a patient develops a temporary contraindication (e.g. temporary tissue expanders in breast cancer patients) after the baseline MRI, follow up MRIs will be discontinued for safety for the duration in which the patient has a contraindication. However, once the patient is no longer contraindicated to receiving MRIs, the study schedule may resume with their next scheduled MRI time point from date of enrollment. Therefore, some time points may be skipped during the patient's enrollment in the study.

Also, if a patient needs a repeat MRI at any time point for any reason (i.e. panic attack during the MRI causing them to not be able to continue, unreadable images, etc.), we may repeat the MRI as long as the patient is willing.

5.6. Duration of the study for the subject

Based on an enrollment of 40 evaluable patients (a subset of the approximately 700 SURVIVE Registry patients enrolled annually across all SURVIVE participating sites) who demonstrate moderate to high risk of cardiotoxic effects during cardio-oncology treatment due to observed segmental dysfunction at baseline, it is anticipated that all subjects will be enrolled within 12 months after study initiation. The study will end when the last enrolled subject completes the 36-month follow-up, data is analyzed and reports are written. Therefore, study duration is anticipated to be approximately 54 months.

5.7. Sample size

40 evaluable patients will be randomized 1:1 to the MyoStrain® imaging guided arm versus the standard of care arm.

5.8. Enrollment

Subjects are considered to be enrolled in the study after they have signed the IRB approved PROACT informed consent form. No investigational tests will be performed before this moment.

6. INFORMED CONSENT

6.1. Consent for Study Participation

All subjects recruited for study participation must meet all study enrollment inclusion/exclusion criteria prior to being enrolled in the study. Once compliance with study inclusion/exclusion criteria is confirmed and the Investigator has determined that a subject is potentially eligible for study participation, the subject may be asked to participate in the study. Informed consent must be obtained from all subjects prior to study participation. The Informed Consent must be approved by the Institutional Review Board (IRB)/Ethics Committee (EC) overseeing the conduct of this study. Each original signed informed consent will be retained in the subject's study records and a copy of the consent should be provided to the subject.

6.2. Subject withdrawal

Subjects can withdraw informed consent at any time during the study. Subjects who withdraw informed consent will not be replaced and the data will not be analyzed (per protocol analysis, see section "statistical considerations"). Subjects discontinuing participation in the study upon written notification before completion of the predefined follow-up will have their data (baseline and interim follow-up intervals) imputed from analysis.

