1.3. Study Design

This is a prospective, multi-center, open label, randomized study. The study will enroll patients who exhibit subclinical myocardial dysfunction at baseline as determined by MyoStrain® evaluation.

Patients with any type of cancer scheduled to receive anti-cancer therapy, who are previously enrolled in the SURVIVE Registry, will be screened for study participation. Consented subjects meeting all inclusion/exclusion criteria will be enrolled into the PROACT study. Subjects will be randomized 1:1 between the MyoStrain® guided treatment arm and MyoStrain® observational arm. Patients in both randomized study arms will be followed with MyoStrain® testing at baseline, 1, 3, 6, 12, 24 & 36 month follow-ups, as outlined in the protocol.

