importance of MyoStrain cardiac features compared to cardiac toxicity risk prediction based on standard assessment of variables LVEF, LVESV, LVEDV, and LV Stroke Volume Index (LVSVi). Endpoints will be evaluated based on discrete variables of MyoStrain values versus standard assessments. Considering many patients will have a complex management of cardioactive medications as well as cancer treatment regimen, the classification of cardiotoxicity status will be based on a clinical committee to designate whether the patient experienced no cardiotoxicity, functional decline without cardiotoxicity, subclinical cardiotoxicity, or clinical cardiac dysfunction at each exam timepoint. The last analysis will help to identify also any indication for interactions among variables studied. We will implement Intention-To-Treat-analysis, where the analyses of the two groups will be based on the initial treatment assignment in the two randomized groups. If in the follow-up data-points may be missing, we will check if the missing data-points are random and if several covariates can help in imputation of missing. We plan to use MI procedure of SAS Institute for such imputations. The regression will be implemented via GLM, LOGISTIC and MIXED (for statistical analysis of repeated measures) procedures in SAS. For mixed models, a comparison of models will be done via likelihood ratio test and by using the Akaike Information Criterion (AIC) and Schwartz's Bayesian Criterion (SBC). Graphical presentations will be implemented in R via LMER of LME4 mixed modelling build in functions, and specialized software GGPlot2 in R. Decision (known also as partition) trees will be implemented with SAS-Data Mining software. We will use also PYTHON-scikit machine learning package for testing the performance of partition-trees via random forest. A random forest is a meta estimator that fits a number of decision tree classifiers on various sub-samples of the dataset and use averaging to improve the predictive accuracy and control overfitting.

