Based on pilot data and utilizing only the moderate to high risk group (>2 segments of Myostrain determined segments >17%), the outcome expected would be 12.8 +/- 4.7 dysfunctional segments for the intervention group and 16.8 +/- 7.8 dysfunctional segments for the control group (and using average of 4.7 and 7.8 for the standard deviation for the overall outcome) at 6 months. This same parameter will be followed at the other time points, including 1 year, 2 years, and 3 years, but the primary endpoint will be at 6 months. With these calculations, 102 patients are required to have a 90% chance of detecting, as significant at the 5% level, a decrease in the primary outcome measure from 16.8 in the control group to 12.8 in the experimental group (number of dysfunctional segments (>17%)).

The sensitivity, specificity, and diagnostic accuracy of each reader to detect changes in myocardial function will be determined for quantitative SENC-CMR. Cutoff-values used to calculate sensitivity and specificity of the quantitative SENC parameters were determined using data previously published. The cutoff for the % of MyoStrain segments <= -17% (based on 37 left ventricular segments) in detecting subclinical cardiotoxicity in the PREFECT50 planned interim analysis was 68% and the cutoff for detecting clinical cardiac dysfunction was 49%; a cutoff of 80% differentiates normal cardiac function from patients experiencing functional decline. McNemar's test with continuity correction will be used to compare the diagnostic performance of each of the SENC-CMR cutoff parameters. Additionally, Receiver Operating Characteristic curves as well as Precision Recall curves will be generated to calculate and compare the area under the curves to determine the diagnostic performance of changes in strain parameters and standard assessments. Inter- and intra-observer variability will also be determined for each of the above parameters using intraclass correlation.

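### Section 6.2 leaves consent withdrawals out of the analysis under a per-protocol rule that Section 11 does not contain, and its rule for other discontinuations is ambiguous

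*Combined protocol and SAP*

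**What the plan says.** Section 6.2 (Subject withdrawal) has two rules.

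- Withdrawal of consent: "Subjects who withdraw informed consent will not be replaced and the data will not be analyzed (per protocol analysis". The parenthesis goes on to refer the reader to the statistical considerations. No time limit is put on the data concerned.
- Discontinuation on written notification before the end of follow-up: such subjects "will have their data (baseline and interim follow-up intervals) imputed from analysis".

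Section 6.2 does not say how the two situations differ, so one patient could fall under either rule.

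Section 11 (Statistical Considerations) says: "We will implement Intention-To-Treat-analysis, where the analyses of the two groups will be based on the initial treatment assignment". On missing data it says "If in the follow-up data-points may be missing, we will check if the missing data-points are random" and whether covariates can help, and then "We plan to use MI procedure of SAS Institute for such imputations". It names no per-protocol analysis or population and no exclusion for withdrawal.

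On timing, the sample-size paragraph of Section 11 follows the number of dysfunctional segments at several visits, "but the primary endpoint will be at 6 months". Section 5.6 adds: "The study will end when the last enrolled subject completes the 36-month follow-up". Section 1.3 describes the design: "This is a prospective, multi-center, open label, randomized study".

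**The concern.** The two sections give an analyst different instructions for the same patient. Section 11 analyses patients in the arm to which they were randomised and plans to impute missing follow-up. Section 6.2 leaves out those who withdraw consent and justifies this by an analysis that is not there.

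The outcome used for the sample size is measured at 6 months, but patients can withdraw up to month 36. A patient with a valid 6-month scan who withdraws consent at month 20 would, on the natural reading of 6.2, lose that observed outcome. This is selection on a post-randomisation event. Physicians in the guided arm see the MyoStrain values and those in the observational arm do not (Section 5.1), so withdrawal might differ by arm and might be related to cardiac course. If both held, the comparison of arms would be biased. With few patients and no replacement, there would also be some loss of power.

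The second rule has a different problem: two analysts could follow it in good faith and obtain different analysis sets.

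**Working it through.** **1. The text, side by side**

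| Question | Section 6.2 | Section 11 |
|---|---|---|
| Principle | Per protocol, by cross-reference | Intention-to-treat by initial assignment |
| Consent withdrawn | Data not analysed, no time limit | No exclusion stated |
| Discontinued in writing | Baseline and interim data are imputed from analysis | Missing follow-up points checked, then imputation planned |
| What is imputed | Apparently data already collected | Only missing follow-up points |

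Section 11 appears in full apart from a figure, and no removed page falls within it, so the absence of a per-protocol analysis is not a redaction effect. Both sections are current text, not amendment-log text.

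The phrase on imputation has two workable meanings: (a) omit the baseline and interim values; (b) keep them and impute later visits. Meaning (b) would agree with Section 11, but the words in the parenthesis, baseline and interim follow-up, fit it poorly because those are the visits already observed.

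**2. The plan's own figure**

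Inputs from Section 11: means 16.8 and 12.8, difference 4; SD (4.7 + 7.8)/2 = 6.25; 5% level, taken as two-sided; 90% power.

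n per arm = 2 × [6.25 × (1.960 + 1.282)/4]² = 51.3. That is 102 in total if rounded down and 104 if rounded up. The stated 102 reproduces.

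**3. Possible loss of power (illustration)**

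Assumptions not in the documents: the 40 patients of Section 5.7 are the number randomised before attrition; a fraction p leaves by month 36 at a constant rate; a share s of leavers is excluded under 6.2. Power is from the noncentral t distribution, equal arms, difference 4, SD 6.25. With all 40 it is 50.5%.

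- 6-month outcomes if observed data are kept: 40 × (1 − p)^(6/36)
- Observed 6-month outcomes lost under 6.2: s × 40 × [(1 − p)^(1/6) − (1 − p)]

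| p | Outcomes kept | Power if kept | Fall, s = 0.25 | Fall, s = 0.5 | Fall, s = 1 |
|---|---|---|---|---|---|
| 5% | 39.7 | 50.2% | 0.4 points | 0.9 | 1.7 |
| 10% | 39.3 | 49.8% | 0.9 | 1.8 | 3.5 |
| 20% | 38.5 | 49.0% | 1.8 | 3.5 | 7.2 |
| 30% | 37.7 | 48.1% | 2.6 | 5.3 | 11.0 |

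For example, at p = 30% and s = 1, 9.7 observed outcomes are lost, 28 remain, and power is 37.1%. The column s = 1 is an upper bound.

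**4. Possible bias (illustration)**

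Suppose k of 20 control patients are excluded, each one control SD (7.8) from the control mean, and none in the guided arm. The control mean shifts by k × 7.8/(20 − k) = 0.41, 0.87 and 1.38 segments for k = 1, 2, 3. If the excluded patients lie above the mean, the planned difference of 4 becomes 3.59, 3.13 or 2.62; if below, 4.41, 4.87 or 5.38. With s between 0.25 and 0.5, the expected number of lost outcomes is only about 0.2 to 2.4 per arm, so three in one arm, none in the other and all displaced the same way is an extreme case.

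**The case against.** The strongest reply is that withdrawal of consent may itself bar further use of the data. That is possible, and the consent form is not visible here. But 6.2 does not give that reason; it calls the exclusion a per-protocol analysis and sends the reader to a section without one. The point limits the fix and does not remove the contradiction.

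Four stronger readings are tempting, and the documents do not support them.

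- A reader might infer that 6.2 expressly drops all data. It says only that the data will not be analysed. Including data from before withdrawal is the natural reading, since the rule is framed as an analysis-set exclusion, but it remains a reading.
- A reader might infer that the imputation phrase cannot be carried out. It can, in two ways. The fault is ambiguity.
- A reader might infer that Section 11 firmly prescribes multiple imputation for every randomised patient. The plan is conditional on a check of the missing points, and the intention-to-treat sentence speaks of analysis by assigned group without stating that everyone is included.
- A reader might infer that every primary result is at risk. Section 1.5 names a different primary efficacy endpoint, the sensitivity and accuracy of MyoStrain against standard measures. That compares methods rather than arms, so the between-arm bias and power arguments do not apply to it.

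It is also fair to say that the power and bias figures rest largely on assumptions. The scan schedule is the same in both arms (Section 5.1), and nothing in the documents shows that withdrawal will differ. That stands.

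**Conclusion.** Wrong as written. Section 6.2 attributes an exclusion to a per-protocol analysis that Section 11 does not contain and that conflicts with the intention-to-treat principle stated there. Its rule for other discontinuations can be read as two different analyses. This conclusion rests on the text alone and needs no assumed rate.

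The consequence concerns the 6-month comparison of dysfunctional segments between arms. Bias is possible and conditional: it requires withdrawal to differ by arm and to be related to outcome, and the documents give no evidence of either. The loss of power is modest over most of the range, 0.4 to 2.6 points if a quarter of leavers are excluded, and at most about 2 to 11 points if all are. These figures assume 5% to 30% leaving by month 36 at a constant rate and 40 randomised before attrition. The term evaluable is undefined; if it means 40 after exclusions, the calculation does not apply in this form. The matter should be corrected before the arms are compared, but it does not by itself undermine the trial.

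**What to change.** Rewrite 6.2 to agree with Section 11:

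- Data collected before withdrawal or discontinuation stay in the intention-to-treat analysis, unless the subject also withdraws permission to use them. Check this against the consent form.
- Observed values are neither removed nor replaced.
- Later missing visits follow the missing-data procedure of Section 11.
- Delete the reference to a per-protocol analysis and the phrase about imputing from analysis.
- If a per-protocol set is wanted, define it in Section 11 and label it a sensitivity analysis.

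The cost is one amended paragraph and a consent-form check, plus a line in Section 11 if a per-protocol set is kept. If the consent form repeats the 6.2 rule, its wording needs review too. No new data are required.

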7. RISK / BENEFIT ASSESSMENT

7.1. Risks

The SENC MyoStrain® software with the associated pulse sequence patch is a noninvasive imaging technology. There is minimal direct physical risk for imaged subjects as it is an MRI procedure that does not require any invasive intervention or injections. As such the risks are limited to those typical for conventional MRI exams. Subjects will be evaluated for potential contraindications to MRI imaging. Considering image acquisition is very fast (< 5 min) reducing time within the magnetic bore and patients do not need to hold their breath during image acquisition, risks of claustrophobia or anxiety may actually be reduced compared to traditional MRI tests.

7.2. Benefits

The results of the strain analysis provide quantitative assessment of regional function. These measurements will be utilized as observational analysis. Physicians will make clinical decisions using all available clinical information and cardiac test results that are available.

8. ONCORE REGISTRATION PROCEDURES

Patients must not start any protocol intervention prior to registration through the Siteman Cancer Center.

The following steps must be taken in order to register patients to this study:

1. Confirmation of patient eligibility by site PI
2. Consent of patient to PROACT study
3. Confirmation of patient eligibility by Washington University
4. Assignment of Participant ID
5. Registration of participant in the Siteman Cancer Center OnCore database

Once the patient has been entered into the Siteman Cancer Center OnCore database, the coordinating center's coordinator will forward verification of enrollment and the subject ID.

8.1. Confirmation of Patient Eligibility by WUSTL Prior to Registration

Confirm patient eligibility by collecting the information listed below and scanning and emailing it to the coordinating center's coordinator at least one business day prior to the patient's baseline MRI scan:

1. Your name and contact information (telephone number, fax number, and email address)
2. Your site PI's name, the registering investigator's name, and your institution name
3. Patient's race, sex, and DOB
4. Three letters (or two letters and dash) for the patient's initials
5. Currently approved protocol version date
6. Copy of signed consent form
7. Completed eligibility checklist, signed and dated by a member of the study team
8. Copy of appropriate source documentation confirming patient eligibility

The coordinating center will email the participating site with verification of eligibility of the patient within 1 business day. Once verification of eligibility has been received, the patient will be registered into OnCore and the patient may undergo the baseline MRI scan.

